An ACT-Based Physician-Delivered Weight Loss Intervention

Study Protocol

[name], [name], & [name]

July 13, 2016

Study Protocol

The study was approved by the Research Ethics Board (REB-II) at McGill University (Montreal, Canada). Participants provided written informed consent prior to commencing the intervention.

Trial Design

The present study was a two-arm pilot randomized controlled trial conducted from May 7, 2016 to March 7, 2018. Participants were randomized to eight sessions of either an ACT-based intervention aimed at reducing emotional eating or standard care, which involved diet and exercise counselling. All outcomes were assessed at baseline and post-intervention. The present study aimed to recruit 128 participants (64 per condition), similar to the trial protocol outlined by [name] et al. (2014).

Participants

Participants were adults over the age of 18 with overweight or obesity who were seeking treatment for weight loss at a clinic in Toronto, Ontario. Only participants considered to be emotional eaters, as assessed by a score of 3.25 or higher on the Dutch Eating Behavior Questionnaire (DEBQ), were recruited for the study (van Strien, Herman, Anschutz, Engels, & de Weerth, 2012). In addition, participants who did not speak, write, and read in English fluently were excluded from the study, as well as those who were pregnant.

Study Procedures

Participants were recruited upon initial registration at the weight loss clinic. Those who expressed interest to participate were assigned a participant ID number and asked to complete a brief prescreen questionnaire to determine their eligibility based on the criteria described above. Eligible participants were randomly assigned to either the ACT intervention or control condition

based on the ID number they had initially received. Participants completed a battery of questionnaires both baseline and Session 8. Weight was measured every session.

Randomization and Blinding

Participants were randomized in 1:1 sequence using a random number generator (randomizer.org). Two hundred participant ID numbers (1-200) were randomized prior to study commencement and assigned to patients who were prescreened. Due to a high number of ineligible participants, an additional 100 ID numbers (201-300) were randomized during the recruitment process. Participants retained the same ID number throughout, regardless of their eligibility, to simplify the process for administrative staff at the clinics. Participants were blind to their condition, but physicians and administrative staff were not blind to participant condition. Physicians were not blind to participant condition because they were responsible for delivering the ACT intervention or standard care. They were thus required to know the participant's condition in order to deliver the adequate treatment. Administrative staff was responsible for providing physicians with this information and organizing study paperwork and thus needed to be aware of participant condition as well.

Physician Training

Physicians were trained in the delivery of the weight loss interventions in a 1-hour Skype training session delivered by a clinical psychology PhD student. During this training session, each physician was taught how to administer the manualized ACT intervention and provided the opportunity to ask questions pertaining to the various skills that they would be required to teach their patients. Copies of the manual were provided to physicians to follow during sessions. Follow-up training sessions were conducted as necessary to ensure treatment fidelity and clarify questions that arose as physicians began delivering the interventions.

Intervention

Participants in the standard care condition were provided with diet and exercise counselling and psychoeducation from their physicians over the course of 8 sessions, as was routinely done at the clinic. Physicians were responsible for facilitating this counselling at their discretion, and thus what “standard care” entailed differed based on the physician who was administering it. However, standard care did not involve any targeted intervention to reduce emotional eating. Thus, in addition to standard care, participants in the ACT condition were taught techniques to reduce their emotional eating. All sessions were approximately 5-10 minutes in length and weight was assessed at each visit. Three overarching skills were taught over the course of the ACT intervention: (1) values clarification and commitment, (2) metacognitive awareness, and (3) distress tolerance. ACT participants were first taught values clarification and commitment techniques, where they reflected on their reasons for losing weight and how this would improve their quality of life. Participants were taught the BOLD technique (Breathe, Observe sensations, Listen to values, Decide on actions that are in line with values) to use their values to make discussions pertaining to avoiding emotional eating (Ciarrochi, Bailey, & Harris, 2013). Next, participants were introduced to the concept of metacognitive awareness, or recognizing and identifying one’s thoughts, feelings, and emotions. Specifically, participants were trained in mindful eating, in order to increase awareness of hunger and satiety cues and avoid eating when not physically hungry (Kristeller & Wolever, 2011). Lastly, participants were taught to increase distress tolerance in the face of negative emotions that typically led to emotional overeating. Participants were taught acceptance techniques (dropping the rope, urge surfing) to use when experiencing triggering emotions or cravings (Bowen & Marlatt, 2009). An

intervention summary can be found in Table 1 and the intervention manual is available upon request.

Throughout the sessions, physicians formed if-then plans with the patients to specify how to habitually use the ACT techniques to reduce emotional eating in their everyday lives. At the end of each session, participants were given a one-page homework sheet that asked them to monitor their behavior and their use of the ACT techniques during the week. Participants were instructed to bring the homework back with them for the next session so that it could be reviewed with their physician.

Measures

Demographics. At baseline, participants reported basic demographic information including gender, age, English fluency, ethnicity, marital status, educational attainment, employment status, household income, and whether or not they smoked.

Anthropomorphic measures. Weight was measured at each of the eight sessions (primary outcome). Participant body fat percentage was assessed and recorded by their physician at baseline and at completion of the eight sessions (secondary outcome).

Emotional, restrained, and external eating. Participants were pre-screened for emotional eating using the Dutch Eating Behavior Questionnaire (DEBQ; van Strien et al., 1986). The DEBQ is a 33-item questionnaire that assesses three dimensions of eating behaviors: emotional eating (primary outcome), restrained eating (secondary outcome), and external eating (secondary outcome). The emotional eating subscale assesses the reported desire to eat under specific negative emotional conditions such as stress, anxiety, and depression. The DEBQ has high internal consistency and factorial validity (van Strien et al., 1986). The DEBQ was administered again post-intervention.

Distress tolerance. The Distress Tolerance Scale (DTS; Simons & Gaher, 2005), a brief self-report questionnaire that assesses one's ability to tolerate distressing emotions, was completed at baseline and post-intervention (secondary outcome). The scale is made up of items that assess the dimensions of distress tolerance, absorption, appraisal, and regulation. The DTS has high reliability and high discriminant, convergent, and criterion validity (Leyro, Bernstein, Vujanovic, McLeish, & Zvolensky, 2011; Simons & Gaher, 2005).

Mindfulness. At both time points (i.e. baseline, post-intervention) participants completed the Philadelphia Mindfulness Scale (PHLMS; Cardaciotto, Herbert, Forman, Moitra, & Farrow, 2008), a 20-item self-report questionnaire that assesses two components of mindfulness: present-moment awareness and acceptance (secondary outcome). The scale has been shown to have good internal consistency and construct validity (Cardaciotto, Herbert, Forman, Moitra, & Farrow, 2008).

ACT application. At baseline and post-intervention participants filled out a self-report questionnaire designed to assess the extent of the participant's use of ACT strategies to reduce emotional eating (secondary outcome). This questionnaire was developed for the present study to evaluate participants' real world application of the intervention. Participants were asked to indicate their level of agreement on a 5-point scale (1 = strongly agree and 5 = strongly disagree) to prompts such as "My values motivate me to lose weight" and "I am able to accept negative emotions and don't have to eat when I'm feeling bad".

Treatment satisfaction. After the eighth session, participants completed a brief, self-developed questionnaire to assess their overall satisfaction with the intervention. Participants were asked to indicate their level of agreement on a 5-point scale (1 = strongly agree and 5 = strongly disagree). Physicians were also asked to complete a similar questionnaire at various

points throughout the intervention to obtain their input on its feasibility and efficacy of the intervention. Open-ended feedback was also collected from physicians, asking for their suggestions on ways to improve the intervention, and to provide insight on patient dropout/non-responsiveness.

Data Analysis

All analyses were conducted in SPSS version 24. 2 Two separate 2 (Condition: Standard Care, ACT Intervention) x 2 (Time: Baseline, Session 8) repeated measures MANOVAs were conducted for the anthropomorphic and questionnaire data outlined above, respectively, with follow-up *t*-tests conducted as necessary. Two separate MANOVAs were conducted to not lose data from incomplete cases (i.e., participants who had completed anthropomorphic but not questionnaire data). Independent samples *t*-tests were conducted for treatment satisfaction data collected at Session 8, whereas chi-square tests were conducted to compare recruitment rates, attrition rates, questionnaire completion, and intervention completion time between conditions. Missing data were not imputed because of the large drop out rates: Imputation with small sample sizes and high rates of missingness has been shown to be highly prone to Type I error (McNeish, 2016).

References

- Bowen, S., & Marlatt, A. (2009). Surfing the urge: brief mindfulness-based intervention for college student smokers. *Psychology of Addictive Behaviors, 23*(4), 666-671.
- [name], B., Ivanova, E., Xu, Z., Chamandy, M., Lowensteyn, I., Joseph, L., Luszczynska, A., & Grover, S. (2014). Increasing the effectiveness of the Diabetes Prevention Program through if-then plans: Study protocol for the randomized controlled trial of the McGill CHIP Healthy Weight Program. *BMC Public Health, 14*, 470.
- Kristeller, J., & Wolever, R. Q., (2011). Mindfulness-based eating awareness training for treating binge eating disorder: the conceptual foundation. *Eating Disorders, 19*(1), 49-61.
- Leyro, T. M., Bernstein, A., Vujanovic, A. A., McLeish, A. C., & Zvolensky, M. J. (2011). Distress Tolerance Scale: A confirmatory factor analysis among daily cigarette smokers. *Journal of Psychopathology and Behavioral Assessment, 33*(1), 47-57.
- Simons, J. S., & Gaher, R. M. (2005). The Distress Tolerance Scale: Development and validation of a self-report measure. *Motivation and Emotion, 29*(2), 83-102.

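### The DEBQ emotional eating outcome (primary, with weight) is collected after baseline only at Session 8, so the planned comparison is among completers and is not protected by randomization

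*Combined protocol and SAP*

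**What the plan says.** Measures gives the DEBQ subscales this status: "emotional eating (primary outcome), restrained eating (secondary outcome), and external eating (secondary outcome"). Weight is the other primary outcome: "Weight was measured at each of the eight sessions (primary outcome").

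Study Procedures sets the questionnaire timing: "Participants completed a battery of questionnaires both baseline and Session 8". Measures adds "The DEBQ was administered again post-intervention", and Data Analysis defines the second time point in the same way: "2 (Condition: Standard Care, ACT Intervention) x 2 (Time: Baseline, Session 8) repeated measures MANOVAs were conducted". Read together, the post-intervention DEBQ is the Session 8 DEBQ.

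On missing data, Data Analysis states: "Missing data were not imputed because of the large drop out rates". It also explains why anthropomorphic and questionnaire data are analysed separately: "Two separate MANOVAs were conducted to not lose data from incomplete cases (i.e., participants who had completed anthropomorphic but not questionnaire data"). On attrition it states that "chi-square tests were conducted to compare recruitment rates, attrition rates, questionnaire completion, and intervention completion time between conditions".

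No section describes an interim DEBQ, collection from people who have stopped attending, or a sensitivity analysis for them.

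**The concern.** Reaching Session 8 happens after randomization, and the assigned arm could influence it. According to Intervention and Table 1, ACT adds techniques to sessions of 5 to 10 minutes and sets homework after each one. If the people who stay differ between arms in ways related to change in emotional eating, the completer difference mixes the effect of ACT with the effect of who stayed.

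The gap matters more for the DEBQ than for weight. By the end of Session 5, Table 1 has covered values, BOLD, dropping the rope and urge surfing. A participant who stops then has received much of the ACT content and has several weights on record, but has no described post-baseline DEBQ and adds nothing to that primary comparison.

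**Working it through.** **1. Who is analysed.** A 2 x 2 repeated measures MANOVA on Baseline and Session 8, without imputation, needs both values. The stated reason for splitting the MANOVAs confirms that a participant without questionnaire data is absent from the questionnaire analysis. The analysed set may be narrower than Session 8 attenders: some may attend without completing the questionnaires, and a MANOVA across all scales removes anyone missing one of them.

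**2. Figures available.** The plan has no retention or bias figure to reproduce. Trial Design gives a target of 64 per condition without alpha, power, effect size, SD or dropout allowance, so 64 is used here only as an input. All retention rates and correlations below are assumptions.

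**3. Model.** Take no true effect, DEBQ change with SD 1, and a normally distributed tendency to stay that has correlation rho with that change. If a fraction p stays, the mean change among stayers shifts by rho x phi(z_p)/p, where phi(z_p) is the normal density at the cut-off. The factor phi(z_p)/p is 1.159 at p = 0.3, 0.966 at 0.4, 0.798 at 0.5 and 0.644 at 0.6. The spurious difference is the shift in one arm minus the shift in the other.

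**4. Lead scenario, 40% versus 60% retained.**
- Difference in factors: 0.966 - 0.644 = 0.322.
- rho = 0.3: 0.3 x 0.322 = 0.097 SD. rho = 0.5: 0.5 x 0.322 = 0.161 SD.
- Stayers: 64 x 0.4 = 25.6 and 64 x 0.6 = 38.4. Standard error: sqrt(1/25.6 + 1/38.4) = 0.255, or about 0.26 SD.
- Bias over standard error: k = 0.38 and 0.63. Type I error, Phi(k - 1.96) + Phi(-k - 1.96), is about 7% and 10%, against a nominal 5%.

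**5. How far the answer moves with the assumptions.**

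| Retention | Correlation | Spurious difference (SD) |
|---|---|---|
| Equal | Same in both arms | 0 |
| 40% v 60% | 0.3 to 0.5, both arms | 0.097 to 0.161 |
| 30% v 60% | 0.3 to 0.5, both arms | (1.159 - 0.644) x rho = 0.155 to 0.258 |
| 50% both | Differs by 0.2 between arms | 0.2 x 0.798 = 0.16 |
| 50% both | 0.4 in one arm, 0 in the other | 0.4 x 0.798 = 0.32 |

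In the last row the standard error is sqrt(2/32) = 0.25 SD, so the bias exceeds one standard error and the type I error is about 25%. The first and last rows both have equal retention, so a chi-square test of attrition could not tell them apart.

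**The case against.** The strongest reply is that harm is not demonstrated. The documents give no dropout rate and no difference between arms. Equal retention with the same mechanism gives no bias, and in the lead scenario the bias is smaller than the sampling error. The trial is a pilot. Attrition and questionnaire completion are compared between arms, and Measures has physicians comment on dropout, so differential loss would be visible. All of this stands as a limit on size. It does not remove the point. The plan names primary efficacy outcomes and tests them between arms, and describing the loss does not correct for it.

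The plan's reason for not imputing concerns imputation in small samples. It does not bear on whether the scale could have been collected from those who stopped.

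Three stronger readings are tempting, and the documents do not support them:
- A reader might infer that people who stopped were never contacted and were treated as having left the study. The text is silent on this. Attrition and questionnaire completion are listed as separate comparisons, and the supportable statement is that no off-schedule collection is described.
- A reader might conclude that the DEBQ result is biased, or that randomization has been undone. A completer comparison lacks the protection of randomization, which makes bias possible without proving it.
- A reader might conclude that no analysis could use the leavers. They have baseline scales, demographics and interim weights, which could support an analysis under a stated missing-at-random assumption, probably with little gain. What they lack is an observed post-baseline DEBQ.

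**Conclusion.** The point holds in this form. As the protocol is written, the DEBQ emotional eating comparison is restricted to participants who reached Session 8 and completed the questionnaires. It is not protected by randomization, and nothing in the plan corrects for the loss or tests sensitivity to it.

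The size and direction of any bias cannot be derived from the documents. The lead scenario gives about 0.10 to 0.16 SD against a standard error of about 0.26 SD. The wider set of assumptions runs from zero to about 0.3 SD. These figures rest on a bivariate-normal selection model, 64 randomized per arm, and assumed retention rates and correlations. The conclusion about who is compared needs none of those assumptions.

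**What to change.** 1. **Collect from those who stop.** Define a time window after randomization for the final DEBQ, the same in both arms. The window must be written down, because the protocol states no session interval and plans to compare intervention completion time between arms. Send the self-completed emotional eating subscale by mail or e-mail to every eligible randomized participant who has stopped, and include the responses in the comparison by assigned arm. Do not route this through clinic staff, who are unblinded according to Randomization and Blinding.

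2. **In all cases, report the result for what it is.** Label the Session 8 DEBQ result a completer result. Show baseline characteristics of completers and leavers by arm. Report the comparison under a stated range for leavers, from no change to the same change as completers, varied by arm. If completers in an arm change by D, a fraction p is retained, and leavers have a share k of that change (k from 0 to 1), the arm mean is D x [p + k(1 - p)]. As an illustration, take the same D in both arms, with 40% retained in ACT and 60% in standard care. The completer difference is then 0. The range runs from 0.4D - D = -0.6D (k = 0 in ACT, 1 in standard care) to D - 0.6D = 0.4D (the reverse). The range does not cover leavers who got worse, and the report should say so.

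A mid-course DEBQ is not recommended. Table 1 uses DEBQ results as ACT material in Session 1, so repeating the scale in standard care could draw attention to behaviour that only ACT targets. A Session 4 value would also come before urge surfing and mindful eating.

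The text is in the past tense and gives an end date of March 7, 2018. If data collection is complete, only step 2 applies, and it needs no new data. The costs of step 1 are incomplete response, a different mode of completion for some participants, and a small administrative cost.

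### The arm is fixed by an ID issued before the prescreen, clinic staff are not blind, and no step withholds the ID-to-condition link, so the procedure permits foreknowledge of the arm at enrolment

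*Combined protocol and SAP*

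**What the plan says.** **Order of events (Study Procedures).** Recruitment takes place at first registration at the clinic. "Those who expressed interest to participate were assigned a participant ID number and asked to complete a brief prescreen questionnaire to determine their eligibility". Then "Eligible participants were randomly assigned to either the ACT intervention or control condition", "based on the ID number they had initially received".

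**Source of the list (Randomization and Blinding).** Allocation is 1:1 from an online random number generator. "Two hundred participant ID numbers (1-200) were randomized prior to study commencement and assigned to patients who were prescreened". Later, "Due to a high number of ineligible participants, an additional 100 ID numbers (201-300) were randomized during the recruitment process". On keeping one number per person: "Participants retained the same ID number throughout, regardless of their eligibility, to simplify the process for administrative staff at the clinics".

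**Who knows the arm (same section).** Participants are blind, but "physicians and administrative staff were not blind to participant condition". "Administrative staff was responsible for providing physicians with this information and organizing study paperwork".

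**Consent.** The opening paragraph of the protocol places written consent before the intervention begins. It does not place it relative to the issue of the ID or the assignment of condition.

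**Concealment.** No section mentions envelopes, an outside list holder, or a rule on when the link between ID and condition may be opened.

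**The concern.** Randomization protects against selection only if those who recruit cannot know the next assignment. Here a patient already holds the number that fixes the arm before eligibility is known, and the staff role that the single-number scheme is meant to help is unblinded. If whoever issues IDs or encourages participation can look up the condition, entry to each arm can depend on the arm, through who is encouraged to take part or which number a given patient is handed.

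The main analysis gives only partial protection. The Condition x Time test removes a stable between-arm difference in level. It does not remove selection on a factor related to change, such as motivation to lose weight. The conclusions at stake are those on the primary outcomes, weight and emotional eating.

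**Working it through.** **Step 1. Set the text side by side.**

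| Element | What the protocol establishes | What it leaves open |
|---|---|---|
| Time of ID issue | Before the prescreen result | Who issues it |
| What fixes the arm | The ID first received | When the condition is looked up |
| List | IDs 1-200 randomized before the start, 201-300 during recruitment | Who holds it |
| Unblinded roles | Physicians and administrative staff | When they first learn the condition |
| Consent | Before the intervention | Whether before allocation |

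Randomizing IDs early is unbiased if the link is hidden. Unblinded staff are unavoidable once treatment starts. It is the combination with no stated withholding step that permits foreknowledge.

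**Step 2. Possible size of bias.** The plan gives no figure on this point to reproduce. From the plan I take only the target of 128 (64 per arm) and the 300 IDs. The rest is assumed: a fraction q of eligible patients, those lowest on a selection factor, is lost from one arm, and the factor correlates r with change.

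Shift in mean change, in SD units = r x phi(z_q) / (1 - q), where phi is the standard normal density and z_q the q-quantile. The multiplier phi(z_q)/(1 - q) is 0.109, 0.195 and 0.350 for q = 0.05, 0.10 and 0.20.

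| r | q = 0.05 | q = 0.10 | q = 0.20 |
|---|---|---|---|
| 0 | 0 | 0 | 0 |
| 0.1 | 0.011 | 0.020 | 0.035 |
| 0.2 | 0.022 | 0.039 | 0.070 |
| 0.3 | 0.033 | 0.058 | 0.105 |

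**Step 3. False-positive rate.** For a single outcome, the 2 x 2 interaction equals a two-sided 5% t-test on change. With n per arm, the noncentrality is shift / sqrt(2/n). In the worst cell at n = 64 it is 0.105 / 0.177 = 0.59 on 126 degrees of freedom, which gives 9.1%.

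| r | 64 per arm, q = 0.05 / 0.10 / 0.20 |
|---|---|
| 0.1 | 5.0 / 5.1 / 5.4% |
| 0.2 | 5.2 / 5.6 / 6.8% |
| 0.3 | 5.4 / 6.2 / 9.1% |

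Data Analysis reports large drop-out. At an assumed 40 or 30 analysed per arm, the worst cell falls to 7.5% or 6.9%.

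**Step 4. Would the planned recruitment-rate test show it?** Data Analysis plans a chi-square comparison of recruitment rates but does not define the denominator. Take 128 enrolled and an equal split of the denominator between conditions. The denominator is all 300 IDs, or an assumed 200 or 160 eligible patients. Exact binomial power of the Pearson test at 5%:

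| Relative shortfall in one arm | 300 | 200 | 160 |
|---|---|---|---|
| 10% | 13% | 17% | 27% |
| 20% | 40% | 56% | 82% |

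A 10% loss would usually be missed, but it biases change by at most 0.06 SD. A 20% loss would be missed 18-60% of the time. Steering which patient gets which ID leaves the enrolment rates equal, so the test would flag it only at its roughly 5% error rate. I have no estimate of the bias from steering.

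**Step 5. Precision of a retrospective check.** The 95% half-width for the difference in enrolment rates with no shortfall is 1.96 x sqrt(2p(1 - p)/m), with p = 128/N and m = N/2. For N = 200 this is 1.96 x sqrt(2 x 0.64 x 0.36 / 100) = 13.3 percentage points. For N = 300 it is 11.2, and for N = 160 it is 12.4.

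**The case against.** The strongest reply is that foreknowledge is inferred from silence. The protocol does not say who issued IDs, scored the prescreen or held the list. It explains unblinding mainly by tasks that come after enrolment. Its statement that eligible participants were assigned also fits a look-up made only after eligibility. All of this stands. A reader might infer that staff held the list at prescreen, or that enrolment was in fact selective; the documents support neither. They also do not show that consent followed allocation. They say only that it came before the intervention, and the consent pages are not in the file. What survives is narrower: the stated procedure ties the arm to a number held before eligibility is known, and no stated safeguard prevents an earlier look-up.

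Existing features do limit the risk. Entry needs a self-reported DEBQ emotional eating score of at least 3.25, participants are blind, and no motive for selection is documented. These do not govern who is encouraged to take part or which ID is handed out.

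The figures are also open to challenge. Every selection input is assumed, patients are taken to be ranked perfectly on the factor, and a single-outcome test stands in for the planned MANOVAs. That is fair. The figures show scale only, and most cells are small. Finally, the text is in the past tense with an end date of March 7, 2018, so a change in allocation probably cannot reach this trial.

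**Conclusion.** The point holds as a statement about what the procedure permits. The arm is knowable from an ID issued before the prescreen, unblinded clinic staff work with that ID, and no withholding step is described. Under assumed one-sided loss of 5-20% of eligible patients and a correlation of 0.1-0.3 with change, bias is about 0.01-0.10 SD of change, and it is zero if the selection factor is unrelated to change. The false-positive rate stays at or below 6.8% at 64 per arm, except in the worst cell (9.1%). The case for action rests on the missing safeguard and the low cost of supplying it, not on a large projected bias. A non-significant recruitment-rate test would not rule selection out. Confidence is moderate: a clear statement that the link was held outside the clinic until enrolment was complete would settle the matter.

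**What to change.** **For any enrolment still to come, or a follow-on trial.** Use the prescreen ID as an administrative label only. Assign condition 1:1 from sequentially numbered sealed envelopes, or from a separate list held outside the clinic, opened only after eligibility, written consent and baseline measures are recorded. The cost is an envelope set or an outside list holder, one administrative step per participant, and the loss of the single-ID convenience.

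**For participants already enrolled.**
- State who held the list and when the link was released to clinic staff.
- Tabulate prescreened, eligible, consented and enrolled counts, and baseline characteristics, by the condition attached to the ID.
- Give the difference in enrolment rates among eligible patients with a 95% confidence interval, and note that this cannot detect steering of IDs.
- If the link was not hidden from clinic staff, report lack of allocation concealment as a limitation on the between-arm conclusions.

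Because ineligible patients kept their IDs, the tabulation should come from existing ID and prescreen records, with no new data collection.

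### Should the outcome analyses carry a physician term because standard care differed from one physician to another?

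*Combined protocol and SAP*

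**What the plan says.** - **Intervention:** counselling was left to the physician's judgment, and what standard care "entailed differed based on the physician who was administering it". The ACT arm had it too: "in addition to standard care, participants in the ACT condition were taught techniques to reduce their emotional eating". Patients received counselling and "psychoeducation from their physicians over the course of 8 sessions", which leaves open whether each patient kept one physician.
- **Study Procedures:** "Eligible participants were randomly assigned to either the ACT intervention or control condition", by the ID number already held. Randomization is therefore by patient, not by physician.
- **Randomization and Blinding:** physicians were unblinded because "they were responsible for delivering the ACT intervention or standard care". "Administrative staff was responsible for providing physicians with this information".
- **Physician Training:** "each physician was taught how to administer the manualized ACT intervention".
- **Measures (treatment satisfaction):** "Open-ended feedback was also collected from physicians", but no count of patients by physician is planned.
- **Data Analysis:** two repeated measures MANOVAs with condition and time as the only factors, then t-tests. There is no physician factor. The document does not give the number of physicians or how patients came to them.

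**The concern.** The plan names something that may make outcomes vary and then leaves it out of every model. In a trial delivered by physicians, a reader expects either a physician term or a reason for having none.

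Two things could be at stake. The first is precision: if physicians differ in how much their patients change, that variation sits in the error term, and the plan already reports heavy dropout. The second is validity: if ACT patients tended to go to particular physicians, the arm comparison would partly be a comparison of physicians. Staff knew the condition and the rule for assigning physicians is not described, so the document does not rule this out in so many words.

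**Working it through.** **1. Inputs.** From the document: 128 patients planned, 64 per arm, individual 1:1 randomization, two analysis time points, and dropout called large without a rate. Assumed, because the document gives no figure: 4, 6 or 8 physicians (4, 8 or 16 in a second set of runs); 64, 32 or 16 completers per arm; intraclass correlation (ICC) of 0 to 0.20 for change; outcome SD 1. The plan has no physician-related figure to reproduce.

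**2. What the planned test compares.** With two time points, the condition-by-time test compares mean change between arms. Write baseline as p + L + e0 and Session 8 as p + L + C + arm effect + e1, where p is the patient, L the physician's effect on level and C the physician's effect on change. The difference is C + arm effect + (e1 − e0), so L cancels. A generalized least squares check with residual variance 0.49 and 64 per arm confirms this. The variance of change is 2 × 0.49 = 0.98, so SE = √(0.98 × 2/64) = 0.175. The fitted SE was 0.175000 and the estimate −0.038715 at every physician-level variance tried (0, 0.05, 0.16, 1.0). A physician intercept added to the condition-by-time model therefore does nothing to this test. Only a model of change, or of Session 8 adjusted for baseline, could.

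**3. Level of the planned tests.** Change was simulated as a + e, with var(a) = ICC, var(e) = 1 − ICC, no arm effect, and physician independent of arm. Both arms then draw on the same mix of physicians.

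- t-test, 64 or 32 per arm, 20,000 trials per setting: type I error 4.7% to 5.3% (Monte Carlo SE √(0.05 × 0.95/20,000) = 0.15 points).
- MANOVA condition-by-time test with 2 or 7 outcomes: 4.8% to 5.3%.
- Separate runs with 4, 8 or 16 physicians, 64 per arm, ICC 0.05 to 0.10: 4.6% to 5.1%.

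**4. Precision from a random physician intercept on change.** VR is the unadjusted variance divided by the adjusted variance. SE reduction = 1 − 1/√VR, and a negative value is a loss.

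| Assumed ICC | VR, 64 or 32 per arm | SE reduction | VR, 16 per arm | SE reduction |
|---|---|---|---|---|
| 0 | 0.99–1.00 | −0.5% to 0 | 0.98 | −1.0% |
| 0.05 | 1.00–1.02 | 0 to 1.0% | 0.98–0.99 | −1.0% to −0.5% |
| 0.10 | 1.03–1.06 | 1.5% to 2.9% | 1.00–1.02 | 0 to 1.0% |
| 0.20 | 1.12–1.16 | 5.5% to 7.2% | 1.07–1.09 | 3.3% to 4.2% |

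At 64 or 32 per arm, the physician variance is estimated as zero in 22% to 36% of trials at ICC 0.05, and in 8% to 23% at ICC 0.10. The model then falls back to the unadjusted one. A fixed physician factor is riskier: with 16 per arm and 8 physicians its VR is 0.76 to 0.84 at ICC 0 to 0.10, so the SE rises by 1/√0.84 − 1 = 9.1% to 1/√0.76 − 1 = 14.7%.

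**5. What an intercept does not repair.** If the ACT effect itself varied by physician (an assumed 2.5% to 5% of total variance), type I error would be 6.0% to 14.1% unadjusted and 6.2% to 14.5% with physician intercepts. The document does not show such variation, and the intercept would not correct it.

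**6. Burden.** One extra model per outcome means 2 (weight, body fat) + 7 (three DEBQ scales, DTS, two PHLMS components, ACT application) = 9 univariate models.

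**The case for a change.** The strongest case for a change is that crossing of physicians with arm is inferred, not stated. If patients were steered by arm, the planned tests could be badly off. With half the physicians taking 60% of ACT and 40% of control patients, unadjusted type I error is 5.0% to 7.9%; at 75% and 25% it is 6.1% to 22.4% (ICC 0.05 to 0.20). With physicians wholly nested in arm, it is 6.1% to 35.3% (ICC 0.01 to 0.10). A caseload table by arm would separate these cases and costs little if clinic records identify the physician. Dropout could also unbalance physicians among completers, and nothing planned would show it.

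It stands that the document does not state how physicians were assigned, and that a caseload table would be informative. The large error rates do not stand as grounds for a change, because they need arm-dependent assignment, which the document does not show. Staff telling a physician a patient's condition is not evidence that the condition chose the physician, and training every physician in ACT points the other way. Under such steering, physician would also be a post-randomization variable, so adjustment would not be automatically safe. At the 75%/25% split a random intercept still leaves 5.7% to 6.5%.

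The dropout argument for precision also turns round: the fewer the completers, the smaller the gain.

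**Conclusion.** The observation is accurate, but no change to the plan follows. The text says that the content of standard care varied by physician; it does not say that outcomes did, and stable differences in level cancel in the planned contrast.

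On the most natural reading (physicians crossed with arm, assignment unrelated to arm), the planned tests hold their 5% level. A physician term then offers 0 to 3% of the standard error at ICC 0.05 to 0.10 with 64 or 32 per arm, and between a 1% loss and a 1% gain at ICC 0 to 0.10 with 16 per arm. Only at ICC 0.20 is the gain noticeable.

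With few physicians, whether to fit them as random, as fixed or not at all is a choice on which statisticians reasonably differ. For a pilot, leaving them out is a fair trade-off. The number of physicians, how patients reached them and the caseload by arm belong in the trial report; stating them alters no planned analysis or result.

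The conclusion rests on the inferred crossing and on assumed physician numbers, ICC and completer counts. Evidence that assignment followed arm would reopen the question.
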